3.1 Trial Design

This is a multi-centre double blind, placebo-controlled randomized cross-over study comparing 6 weeks of oxytocin treatment to 6 weeks of placebo with a 6-week washout between periods. A phase II adaptive design will be used to efficiently identify promising dose schedules and obtain meaningful efficacy data. In Stage 1 of the study, we will evaluate three dosing schedules compared to placebo: daily dosing, alternate day dosing, and every 3rd day dosing. At the end of Stage 1, Bayesian analysis will be conducted to identify the most promising dose schedule, termed the “target dose”. In Stage 2, additional patients will be enrolled at the target dose schedule. In both stages the primary outcome measure is change on the NPI apathy/indifference domain score from baseline. At the end of Stage 2, data from patients receiving the target dose (from Stage 1 and Stage 2) are combined in the efficacy analysis. An optional CSF sub-study

measuring oxytocin levels during oxytocin vs. Placebo periods will confirm CSF oxytocin level rises in FTD and determine whether changes in CSF oxytocin levels correlate with behavioural measures.

The study is double blinded, participants and all study staff aside from central drug coordinator and unblinded DSMB members will be blinded to dose and arm. In Stage 2 of the study, the study staff and participants will be blinded to dose (at the suggestion of the DSMB and TSC) and arm. Randomization occurs after screening data is accessed and the participant deemed eligible but prior to baseline appointment. In some instances, this meant that participants were randomized into the trial without ever attending a baseline appointment.

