3.6 Timing of outcome assessment

Screening window is 0–28-days followed immediately by Baseline 1 assessments. Initial dose of treatment occurs at baseline appointment but after baseline visit outcome assessments have occurred. Baseline 1 treatment window is 42 days +/- 3 days and then End of Treatment visit 1 assessments occur. The final dose of treatment occurs at the beginning of treatment visit prior to End of Treatment 1 outcome assessments. Then a 42 day +/- 3 days washout. Baseline 2 treatment window is 42 days +/- 3 days and then End of Treatment visit 2 assessments occur. The final dose of treatment occurs at the end of treatment visit 2 prior to outcome assessments.

Section 4: Statistical Principles

The trial has a 2-stage design:

In Stage 1 the trial will compare three dosing schedules of 72 IU intranasal oxytocin (daily, alternate day, or every 3rd day dosing) for patients with FTD compared to placebo. Twenty participants per arm will be randomized to each of the three dose arms and order of the cross-over (order of oxytocin and placebo). All dose schedules will use sprays bid (morning and afternoon, with placebo on non-oxytocin Rx days) to maintain blinding to schedule across all of the cohorts. After 6 weeks, patients will have a 6-week washout period and then cross-over to the other treatment arm (placebo to oxytocin; oxytocin to placebo). After 60 participants have completed their participation, interim Bayesian analysis will determine which of the dosing schedules appears most promising. For Stage 2, the most promising dose schedule, designated the “target dose,” will be carried forward for the remainder of participants n=40 who will complete the exact same procedures as participants in Stage 1. Data from the target dose group from stage 1 and 2 will be combined for the final analysis.

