4.1 Confidence Intervals and P-values

Stage 1 and Stage 2 for the target selected treatment arm will be used to test superiority using a nominal 2.5% one-sided test for the primary outcome of change in NPI.

All secondary, safety and exploratory outcomes will be reported as two-sided tests with statistical significance set at a two-sided 0.05 level.

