4.3 Analysis populations

Intent-to-Treat Population (ITT) - All participants who were randomized and completed at least one baseline assessment.

Modified Intent-to-Treat Population (MITT) - The modified intent-to-treat population is defined as all participants in the ITT Population, but excluding those that did not complete at least one treatment period. Analysis will compare relative period effects for PBO and OXY periods on change in scores from Baseline to End of Treatment.

Per protocol Population (PPP) - All participants who completed each protocol specified study visit and who were at least 70% compliant in study drug administration for both treatment periods. For assessments completed by caregiver, the data must be collected within 30 days of last dose of IP. For cognitive outcomes completed by patient, data must be collected within 3 days of last dose of IP. Data for which there are clear validation errors or where administration errors are clear and unreconcilable for neuropsychological testing will also be excluded from PPP. Exclusion for validation errors will only be possible for IRI and RSMS where such validation errors are apparent.

A CONSORT diagram, detailing the participants excluded from each subsequent population restriction will be presented for the study.

Section 5 – Trial Population

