6.2 Analysis Methods

The primary analysis of the change from baseline NPI apathy domain is based on a linear model with covariates for sex and order of treatment in the crossover including data from both Stage 1 and Stage 2 for the target selected treatment arm (ETD) will be used to demonstrate superiority using a nominal 2.5% one-sided test using the PPP. Estimated mean effect of the treatment compared to placebo and 95% confidence intervals will be reported. Analysis will compare relative period effects for PBO and OXY periods via change in scores from Baseline to End of Treatment visit.

Supportive primary analysis will be conducted on the MITT population. Given the crossover design, the ITT analysis excludes those that did not take any study medications in their second treatment period.

Sensitivity analysis combining all dose groups for OXY vs. PBO will be conducted for all primary, secondary, and exploratory outcome measures.

Covariates:

Order of treatment (End of treatment 2: Oxytocin versus End of Treatment 2: Placebo)

Sex (male vs female)

Subgroup analyses:

By sex

By severity

Age (median split : young <67 years; older 67+ years)

Oxytocin Genetic polymorphism (GG vs AG vs AA)

FTD subtype (bvFTD vs PNFA vs SD)

ALL other outcomes as listed above, will be analysed using the same methods as for the primary outcome using 5% 2-sided test. Subject is modeled as a random effect, the others are all fixed effects.

To explore whether hormonal levels or imaging atrophy patterns predict behavioural response to OXY, we will conduct a linear regression with NPI apathy domain change scores for OXY-PBO as the dependent measure and predictors of regional MRI atrophy ratings (scores from the Harper et al. visual rating scale for each of the following regions: orbitofrontal, rostral anterior cingulate, fronto-insula, medial temporal, and posterior), baseline serum estrogen level (continuous), baseline serum testosterone level (continuous), sex, and treatment order.

The following endpoints are included in the prospective analysis plan:

Table 6.1A. Endpoints for Analysis

#	Endpoint	Role	Endpoint Type	Pop	Model

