1	NPI – Apathy Domain Change Score	Primary Efficacy Endpoint	Continuous Outcome. Higher scores represent worse apathy values.	PPP Most promising dose group (Q3D) from stage 1 and stage 2	$Y_{\text{period}} = \text{Intercept} + \text{subject} + \text{period2} + \text{female} + \text{OXY}$ The intercept covers the reference group of placebo, period #1, and male. The “OXY” is an indicator of treatment – OXY. The Period2 is an indicator of it being the second period. The ‘female’ is an indicator of female patient. Y_{period} represents the NPIA domain score at End of Treatment for that period – score at Baseline for that period
2	NPI – Apathy Domain Change Score	Primary Efficacy Endpoint Supportive Analysis	Continuous Outcome. Higher scores represent worse apathy values.	MITT Most promising dose group (Q3D) from stage 1 and stage 2	$Y_{\text{period}} = \text{Intercept} + \text{period2} + \text{subject} + \text{female} + \text{OXY}$
3	NPI – Apathy Domain Change Score	Primary Endpoint Sensitivity Analysis	Continuous Outcome. Higher scores represent worse apathy values.	PPP – all dose groups combined	$Y_{\text{period}} = \text{Intercept} + \text{period2} + \text{subject} + \text{female} + \text{OXY}$
4	NPI – Apathy Domain Change Score	Primary Efficacy Endpoint Sensitivity Analysis	Continuous Outcome. Higher scores represent worse apathy values.	PPP exclude all new behaviour meds Most promising dose group (Q3D) from stage 1 and stage 2	$Y_{\text{period}} = \text{Intercept} + \text{period2} + \text{subject} + \text{female} + \text{OXY}$
5	NPI – Apathy	Efficacy Endpoint	Continuous Outcome.	PPP	$Y_{\text{period}} = \text{Intercept} + \text{period2} + \text{subject} + \text{female} + \text{OXY}$

	Doman Change Score	SUBGROUP	Higher scores represent worse apathy values.	Most promising dose group (Q3D) from stage 1 and stage 2	BY SEX (M/F)
6	NPI – Apathy Doman Change Score	Efficacy Endpoint SUBGROUP	Continuous Outcome. Higher scores represent worse apathy values.	PPP Most promising dose group (Q3D) from stage 1 and stage 2	$Y_{\text{period}} = \text{Intercept} + \text{period2} + \text{subject} + \text{female} + \text{OXY}$ BY SEVERITY (CDR 0-1 vs 2)
7	NPI – Apathy Doman Change Score	Efficacy Endpoint SUBGROUP	Continuous Outcome. Higher scores represent worse apathy values.	PPP Most promising dose group (Q3D) from stage 1 and stage 2	$Y_{\text{period}} = \text{Intercept} + \text{period2} + \text{subject} + \text{female} + \text{OXY}$ BY AGE (0-65 vs >65)

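### A random subject intercept on period change scores cannot represent a negative within-participant correlation, so the primary 2.5% test may run slightly above its level (about 2.8% to 3.3% if that correlation is between 0 and -0.125)

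*SAP*

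**What the plan says.** - **Response.** In Table 6.1A row 1 the outcome for each period "represents the NPIA domain score at End of Treatment for that period – score at Baseline for that period". Each participant therefore contributes two change scores.
- **Subject term.** Row 1 lists subject beside period, sex and treatment. At the end of the analysis description, section 6.2 states: "Subject is modeled as a random effect, the others are all fixed effects".
- **Narrative description.** The opening sentence of section 6.2 calls the primary analysis a "linear model with covariates for sex and order of treatment in the crossover" and does not mention subject.
- **Population.** The primary analysis uses the per-protocol population (PPP), which section 4.3 defines as follows: "All participants who completed each protocol specified study visit and who were at least 70% compliant in study drug administration for both treatment periods". Every participant in it has both periods.
- **Level.** Superiority is tested "using a nominal 2.5% one-sided test for the primary outcome of change in NPI" (section 4.1).
- **Not stated.** The SAP does not give the estimator, the software, whether the subject variance is bounded at zero, the method for degrees of freedom, or the correlation between a participant's two changes.

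**The concern.** A random intercept is normally there to absorb stable differences between participants. Here the response is already a difference from that period's own baseline, so those stable differences have cancelled. The correlation that remains between the two changes (rho below) can be zero or negative. One reason is that the end of period 1 and the baseline of period 2 are neighbouring visits that enter the two changes with opposite signs.

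A variance component bounded at zero can express only rho of zero or more. When the sample correlation is negative, the fit sets the subject variance to zero and treats the two periods as independent observations. That understates the standard error of the oxytocin effect. When the sample correlation is positive, the model returns the ordinary paired standard error. The error therefore runs in one direction only, towards declaring superiority, and it affects both the primary test and the 95% interval. Because PPP pairs are complete, the random effect recovers no single-period information in exchange.

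**Working it through.** **Inputs from the SAP**
- Nominal level: 2.5% one-sided (section 4.1).
- Sample size: "Twenty participants per arm will be randomized to each of the three dose arms", plus 40 in Stage 2 at the target schedule (Section 4, Statistical Principles). This gives n = 20 + 40 = 60 planned; PPP exclusions would reduce it.
- Visit spacing: "6 weeks of oxytocin treatment to 6 weeks of placebo with a 6-week washout between periods" (section 3.1), so the four assessments are equally spaced, 6 weeks apart.

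**Input assumed**
- rho, the correlation of a participant's two changes, examined from +0.3 to -0.25.

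The SAP derives no figure on this point, so there is nothing of its own to reproduce beyond the nominal 2.5%.

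**Step 1. Which rho is plausible?** Give each visit score unit variance.
- Exchangeable visit scores: the four covariances cancel and rho = 0.
- AR(1) with correlation r between neighbouring visits: covariance = r² - r - r³ + r² = -r(1-r)², and variance of a change = 2(1-r). So rho = -r(1-r)/2, lowest at r = 0.5, where rho = -0.125.
- Correlation that dies out after one 6-week interval: rho = -r/[2(1-r)], which is -0.25 at r = 1/3. This is a stronger assumption.
- Participants who differ in rate of change: adding participant-specific change variance v to the r = 0.5 case gives rho = (-0.125 + v)/(1 + v). This is 0 at v = 0.125 (0.125/1.125 = 11% of the change variance) and +0.2 at v = 0.406 (0.406/1.406 = 29%).

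**Step 2. The two standard errors.** With complete pairs and fixed period, sex and treatment, the oxytocin estimate is the same whatever the variance components. Let W and B be the within- and between-participant mean squares, with expectations s²(1-rho) and s²(1+rho). For equal sequence sizes:
- paired: SE = sqrt(2W/n), on n - 2 = 58 df;
- bounded random intercept (REML): the same SE if B ≥ W, otherwise sqrt(2·[(B+W)/2]/n).

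When B < W the pooled value is below W, so the ratio of the second SE to the first cannot exceed 1.

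**Step 3. Size under no treatment effect.** Simulation, n = 60, 400,000 replicates per row. The df column shows n - 2 throughout, then a Satterthwaite-type choice (n - 2, or 2n - 4 = 116 at the boundary).

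| rho | Mean SE ratio | One-sided size (n - 2 / Satterthwaite) |
|---|---|---|
| +0.3 | 1.000 | 2.5% / 2.5% |
| +0.2 | 0.998 | 2.5% / 2.5% |
| +0.1 | 0.992 | 2.6% / 2.6% |
| 0 | 0.977 | 2.7% / 2.8% |
| -0.125 | 0.942 | 3.2% / 3.3% |
| -0.25 | 0.898 | 3.8% / 4.0% |

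A separate simulation gave 3.1% to 3.2% at -0.125. At rho = 0 the variance is set to zero in 50% of trials. The paired analysis stays at 2.4% to 2.6% at every rho. Results for n = 50 and n = 40 agree within about 0.1 point.

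**Step 4. Large-sample check for negative rho.** Size = 1 - Φ(1.96/√(1-rho)).
- rho = -0.125: 1 - Φ(1.96/√1.125) = 3.23%.
- rho = -0.25: 1 - Φ(1.96/√1.25) = 3.98%.

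Both agree with the simulation.

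**The case against.** **The excess is conditional.** A reader might infer that the primary test simply runs at 2.8% to 4.0%. The SAP does not support that, because it does not give rho. Participants with dementia may well differ in their rate of decline over 18 weeks, and that adds positive covariance. In the most negative AR(1) case, 11% of the change variance from this source brings rho back to zero, and about 29% brings it to +0.2, where the excess has gone. Independent rating error also pulls rho towards zero: with rating-error variance half the AR(1) variance, -0.125 becomes -0.125/2 = -0.0625. This objection stands, and the size must be stated as a range under assumptions.

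**The 4% end is not the natural case.** Serial decay across equally spaced visits stops at -0.125. This also stands.

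**The implementation is not fixed.** The SAP says only that subject is random. An unbounded variance component or a compound-symmetry residual covariance would remove the problem. This is true, but the usual random-intercept fit is bounded, and a plan for a single confirmatory test should not leave the choice open.

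**Is the subject sentence about the primary analysis?** It follows the sentence on other outcomes. However, those outcomes use the primary method, and row 1 contains the subject term. A fixed subject effect would be collinear with sex, so a random intercept is the coherent reading.

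**Reach.** It is tempting to apply the result to every row that shares the formula. It is exact only for complete pairs. The modified intent-to-treat (MITT) rows, including the modelled safety rows 48 to 53, may contain single-period participants and were not examined.

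**Conclusion.** The point holds in a limited form. If the subject variance is bounded at zero, the primary PPP analysis has a standard error at or below the paired one, with an unchanged estimate. With n = 60, the one-sided size is about 2.8% at rho = 0 and about 3.1% to 3.3% at rho = -0.125. It is about 4% only if rho is -0.25, and there is essentially no excess from +0.2 upwards. The conclusion rests on two things the SAP does not state: the value of rho and the zero bound. It concerns the covariance structure only, not any effect of the Stage 1 schedule selection on the level. The likely excess is a few tenths of a percentage point to under one point, always in the direction of declaring superiority. It is worth correcting because the correction is almost free and removes the dependence on rho.

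**What to change.** In section 6.2 and Table 6.1A, specify one of the following, and name the estimator and the method for degrees of freedom.

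1. **PPP analyses:** the period-adjusted within-participant oxytocin-minus-placebo contrast on n - 2 df, equivalent to a fixed subject effect. The sex term then drops out without affecting the treatment contrast.
2. **To keep sex and a single model for PPP and MITT:** replace the random intercept with an unstructured or compound-symmetry residual covariance per participant that allows negative covariance, with Kenward-Roger df. This also uses the data of single-period participants in the MITT rows.

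The cost is one sentence in the SAP and one model option. The result is essentially unchanged when the sample correlation is positive. When it is negative, the interval is somewhat wider. The change in df alone costs about 1% in the critical value (t = 2.002 on 58 df against 1.981 on 116 df; 2.002/1.981 = 1.011).

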Rationale: The IRI is a 28-item study partner questionnaire answered on a 5-point Likert scale that ranges from “Does not describe me well” to “Describes me very well”. The measure has 4 subscales, including an empathic concern scale which looks at feelings of sympathy and concern for others. FTD patients demonstrate deficits in the Empathic concern and Perspective taking subscales. Based on our dose- finding study which demonstrated improvements in empathic concern on the IRI following oxytocin in FTD, we predict that empathic concern scores will be improved following oxytocin administration, demonstrating the efficacy of oxytocin to improve core empathy deficits in patients with FTD.

- Change in the Revised Self-Monitoring Scale (RSMS) score

Rationale: The RSMS is a 13-item study partner completed scale to assess patient’s changes in self-presentation to fit the social setting. The RSMS was added to the new FTLD National Alzheimer’s Coordinating Centers module and will serve as a secondary measure of sensitivity to other’s emotions and the ability of patients to adapt their behaviour accordingly.

- Change in modified Clinicians Global Impression of Change (apathy) (m-CGIC) scores

Rationale: The Clinical Global Impression scale is a 3-item observer-rated scale that measures illness severity (CGIS), global improvement or change (CGIC) and therapeutic response. This modified version includes items directed towards apathy. The CGI is rated on a 7-point scale, with the severity of illness scale using a range of responses from 1 (normal) through to 7 (most severely ill patients). CGI-C scores range from 1 (very much improved) through to 7 (very much worse). Treatment response ratings take account of both therapeutic efficacy and treatment-related adverse events and range from 0 (marked improvement and no side-effects) to 4 (unchanged or worse and side-effects outweigh the therapeutic effects).

- Change in modified Clinicians Global Impression of Change (overall) (m-CGIC) scores

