8	NPI – Apathy Doman Change Score	Primary Efficacy Endpoint SUBGROUP	Continuous Outcome. Higher scores represent worse apathy values.	PPP Most promising dose group (Q3D) from stage 1 and stage 2	$Y_{\text{period}} = \text{Intercept} + \text{period2} + \text{subject} + \text{female} + \text{OXY}$ OXYTOCIN GENE rs53576 AA vs GG vs AG
9	NPI – Apathy Doman Change Score	Primary Efficacy Endpoint SUBGROUP	Continuous Outcome. Higher scores represent worse apathy values.	PPP Most promising dose group (Q3D) from stage 1 and stage 2	$Y_{\text{period}} = \text{Intercept} + \text{period2} + \text{subject} + \text{female} + \text{OXY}$ By FTD clinical subtype: bvFTD vs. svPPA vs. nfPPA
[P u bl is h D at e] 10	EFER	Secondary Efficacy Endpoint	Categorical	PPP Most promising dose group (Q3D) from stage 1 and stage 2	$Y_{\text{period}} = \text{Intercept} + \text{period2} + \text{subject} + \text{female} + \text{OXY}$
11	EFER	Secondary Efficacy Endpoint Sensitivity	Categorical	PPP All doses combined	$Y_{\text{period}} = \text{Intercept} + \text{period2} + \text{subject} + \text{female} + \text{OXY}$
12	EFER	Secondary Efficacy Endpoint Sensitivity	Categorical	MITT Most promising dose group (Q3D) from stage 1 and stage 2	$Y_{\text{period}} = \text{Intercept} + \text{period2} + \text{subject} + \text{female} + \text{OXY}$

13	IRI – Empathic Concern	Secondary Efficacy Endpoint	Continuous outcome. Higher scores represent better values.	PPP Most promising dose group (Q3D) from stage 1 and stage 2	$Y_{\text{period}} = \text{Intercept} + \text{period2} + \text{subject} + \text{female} + \text{OXY}$
14	IRI – Empathic Concern	Secondary Efficacy Endpoint Sensitivity	Continuous outcome. Higher scores represent better values.	PPP – all doses	$Y_{\text{period}} = \text{Intercept} + \text{period2} + \text{subject} + \text{female} + \text{OXY}$
15	IRI – Empathic Concern	Secondary Efficacy Endpoint Sensitivity	Continuous outcome. Higher scores represent better values.	MITT Most promising dose group (Q3D) from stage 1 and stage 2	$Y_{\text{period}} = \text{Intercept} + \text{period2} + \text{subject} + \text{female} + \text{OXY}$
16	IRI - Total Score	Secondary Efficacy Endpoint	Continuous outcome. Higher scores represent better values.	PPP Most promising dose group (Q3D) from stage 1 and stage 2	$Y_{\text{period}} = \text{Intercept} + \text{period2} + \text{subject} + \text{female} + \text{OXY}$

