6.3 Missing Data

NPI apathy is assessed at screening and then at each baseline visit *before study drug administration and at end of treatment visits *after study drug administration.

Schedule: Baseline 1 Visit: 6 weeks on treatment then End of Treatment 1 visit, then 6 weeks washout to Baseline 2 then 6 weeks on treatment and then End of treatment 2 visit.

Missing data will be approached with the assumption that it is Missing at Random. The statistical models incorporate each observed observation and sensors unobserved observations.

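### The primary model analyses raw period change with no baseline term, giving up precision that the period baselines already collected could recover

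*SAP*

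**What the plan says.** Table 6.1A, row 1, states that the response "represents the NPIA domain score at End of Treatment for that period – score at Baseline for that period". The terms are an intercept, subject, an indicator for the second period, an indicator for female sex and an indicator for oxytocin. Section 6.2 names only treatment order and sex as covariates and makes subject a random effect. None of the NPI apathy efficacy rows (1 to 9) has a baseline term, and Section 6.2 carries the same method to the other outcomes.

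The data for adjustment exist. Section 6.3 says "NPI apathy is assessed at screening and then at each baseline visit", before dosing. The primary population is the per-protocol population (PPP), which Section 4.3 defines as "All participants who completed each protocol specified study visit" with at least 70% compliance in both periods. Both period baselines should therefore be available for the primary analysis.

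**The concern.** Subtracting the period baseline fixes its coefficient at 1. That is the most precise choice only if the within-person regression of the end-of-treatment difference on the baseline difference really has slope 1. If the slope is lower, subtraction adds baseline noise to the treatment contrast. The random subject effect does not repair this: it absorbs a person's overall level, not the fluctuation between that person's two baselines.

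At stake is the precision of the primary effect, of its sensitivity and subgroup rows, and of the continuous secondary outcomes. The target-schedule sample is small, and Section 3.4 records funding and enrolment difficulties, so more participants are not an easy substitute. Sample-size planning is left to protocol section 6.1, which is not shown, so how far the planned power already reflects this model cannot be judged.

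**Working it through.** **Inputs from the SAP.** The response and terms are those of row 1, tested one-sided at 2.5%. The planned target-schedule number is 20 (Stage 1) + 40 (Stage 2) = 60 (Section 4). The SAP states no SD, correlation or power, so there is no planned figure to reproduce. The ranges for rho and k below, and the 80% starting power, are assumptions.

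**Formula.** For each person let D_E be the end-of-treatment difference between periods and D_B the baseline difference. Write Var(D_E) = s², Var(D_B) = k·s² and corr(D_B, D_E) = rho.

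- Planned change score: Var(D_E − D_B) = s²(1 + k − 2·rho·√k).
- Baseline-adjusted: residual variance = s²(1 − rho²).
- Efficiency of the planned analysis = (1 − rho²) / (1 + k − 2·rho·√k). It equals 1 only at rho = √k.

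Example: at k = 1 and rho = 0.3 this is 0.91 / 1.40 = 0.65, so 60 participants are worth 0.65 × 60 = 39.

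| k | rho = 0.3 | rho = 0.45 | rho = 0.6 |
|---|---|---|---|
| 1 | 65% (39) | 73% (44) | 80% (48) |
| 0.7 | 76% (46) | 84% (51) | 92% (55) |
| 0.5 | 85% (51) | 92% (55) | 98% (59) |

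Parentheses show what 60 participants are worth relative to the adjusted analysis.

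**Interval width and power.** The adjusted interval is narrower by 1 − √efficiency: 1 − √0.65 = 19% in one corner and 1 − √0.98 = 1% in the other. If the change-score model had 80% power, the adjusted power is Φ((1.96 + 0.84)/√efficiency − 1.96), which runs from 81% to 94%.

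**Cost of the extra term.** About one degree of freedom is spent in the within-person comparison, a variance cost of 1/(n − 4). At n = 60 this is 1/56 = 1.8%. Net efficiency is 66% to 100%, the interval is 0% to 19% narrower, and power is 80% to 93%. Adjustment is worse only for rho of about 0.60 to 0.79 at k = 0.5, 0.75 to 0.90 at k = 0.7, and above 0.965 at k = 1.

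**Simulation checks.**

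- Within-person analysis, 4,000 runs, n = 60, k = 1. The variance ratio of change to adjusted was 1.95 with all correlations 0.5, 1.47 with AR(1) 0.7 and 1.35 with AR(1) 0.9. Both models were unbiased, with type I error 1.9% to 3.0%. The equal-correlation case has rho = 0 and so lies outside the tabulated range.
- Further runs at k = 0.5, 0.7 and 1, with n = 60 and 40, gave ratios of 0.985 to 1.50, unbiased estimates and type I error 2.0% to 2.8%.
- Random-intercept REML, n = 60, effect −0.30 SD. Power rose from 55% to 68% under AR(1) 0.7. With 10% of participants having one usable period (available baseline used, deviation set to zero) it rose from 52% to 65%, with type I error 2.4% to 2.7%.

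**Carryover.** Both models rely on a design "with a 6-week washout between periods". With b = rho/√k, the bias as a share of any carryover at Baseline 2 is:

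- carryover persists to the end of period 2: 0 for the change score, (1 − b)/2 for the adjusted model (0.08 to 0.35 over the assumed range);
- carryover fades by then: 0.50 for the change score, b/2 for the adjusted model (0.15 to 0.42).

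For a carryover of −0.10, a true effect of −0.30, k = 1 and rho = 0.3, simulated estimates were −0.301 (change) and −0.266 (adjusted) if it persists, and −0.354 and −0.316 if it fades.

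**The case against.** The strongest reply is that nothing here is invalid. Change from baseline is specified consistently, the estimate is unbiased without carryover, and the choice between two valid estimators may be taste. The size of the gain is assumed throughout, and its net range reaches zero (k = 0.5, rho = 0.6). An apathy floor at entry could make k less than 1, where gains shrink. If carryover persists, the adjusted estimate is attenuated and the planned one is not. Dose selection has already taken place, and the type I error checks above do not include it. Finally, 60 is the planned count, not the PPP.

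Much of this stands as a limit. Validity is not in dispute, and the range must be read as conditional. The PPP will be smaller than 60, so the participant-equivalents are illustrative; the percentage efficiencies before the extra-term cost do not depend on n, and runs at n = 40 agree. It does not defeat the point. The possible loss from adjusting is at most 1.8% in variance at n = 60, while the possible gain is large. The runs at k = 0.5 and 0.7 show that the result does not hang on k = 1. Carryover can harm either model, so it gives no general reason to prefer the planned one.

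**Conclusion.** The concern holds, as a loss of precision only. Without carryover the planned primary test is valid and its estimate unbiased, but the planned analysis is 66% to 100% as efficient as a baseline-adjusted one, net of the extra term at n = 60. This assumes rho of 0.3 to 0.6 and k of 0.5 to 1, neither of which the SAP supplies. The loss vanishes near rho = √k. The change should be made because the baselines are already collected, and the effect's units and the one-sided 2.5% test stay as they are.

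**What to change.** Before unblinding, keep the change outcome and the terms for subject, period, sex and oxytocin. Add two covariates: the participant's mean period baseline, and the period baseline minus that mean. The oxytocin coefficient remains in NPI apathy points.

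- **Where it applies.** Use it in rows 1, 3 and 4 and subgroup rows 5 to 9, so that primary and subgroup effects come from one model, and in the continuous secondary outcomes with period baselines. Leave out the CGIC rows (23 to 25 and 36 to 39), where the rating is itself a change.
- **One usable baseline.** This can occur in the modified intent-to-treat rows, a population defined by "excluding those that did not complete at least one treatment period". It can also occur in the PPP for the two questionnaires with invalid data: "Exclusion for validation errors will only be possible for IRI and RSMS where such validation errors are apparent". Name one method in the SAP: either the mean of available baselines with the deviation set to zero, or a joint mixed model of all baseline and end-of-treatment scores.
- **Sensitivity analysis.** Report the unadjusted change-score model. It shows dependence on the model but does not remove carryover bias.

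The cost is SAP wording, settled while the statisticians are blinded, as Section 3.5 provides. If the operating characteristics in protocol section 6.1 assumed the change-score model, note the change there. The extra term costs 1/(n − 4) in variance: 1.8% at n = 60, 3.8% at 30, 6.3% at 20 and 17% at 10. Very small subgroup levels, such as may arise in "OXYTOCIN GENE rs53576 AA vs GG vs AG", may gain nothing.
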